**Visit 3 (Week 1):** Vitals will be measured and fasting blood and 24hr urine samples will be collected. Carbohydrate intake/insulin injection logs, food diaries, or CGM/pump data will be reviewed and documented. Patients will be provided with 3 weeks supply of Exenatide extended release or Exenatide extended release placebo and 10mg dapagliflozin or placebo tablets depending on their cohort. Urine collection container will be provided and patients instructed to collect 24hr urine before their next visit. Insulin doses will be titrated to target blood glucose between 70-180 mg/dl if possible at all times without having additional hypoglycemia (less than 70 mg/dl). Ketostix will be dispensed and patients will be instructed to measure ketone bodies in a spot urine sample daily and reported as described in visit 2.

**Visit 4 (Week 4):** Patient physical and vitals will be measured, fasting blood and 24hr urine samples will be collected. Carbohydrate intake/insulin injection logs, food diaries, or CGM/pump data will be reviewed and documented. Patients will be provided with 4 weeks supply of Exenatide extended release or Exenatide extended release placebo and 10mg dapagliflozin or placebo tablets depending on their cohort. Urine collection container will be provided and patients instructed to collect 24hr urine before their next visit. Insulin doses will be titrated to target blood glucose between 70-180 mg/dl if possible at all times without having additional hypoglycemia (less than 70 mg/dl). Ketostix will be dispensed and patients instructed to measure ketone bodies in a spot urine sample daily and reported as described in visit 3.

**Visit 5 (Week 8):** Vitals will be measured and fasting blood and 24hr urine samples will be collected. Carbohydrate intake/insulin injection logs, food diaries, or CGM/pump data will be reviewed and documented. Patients will be provided with 4 weeks supply of Exenatide extended release or Exenatide extended release placebo and 10mg dapagliflozin or placebo tablets depending on their cohort. Urine collection container will be provided and patients instructed to collect 24hr urine before their next visit. Insulin doses will be titrated to target blood glucose between 70-180 mg/dl if possible at all times without having additional hypoglycemia (less than 70 mg/dl). Ketostix will be dispensed and patients instructed to measure ketone bodies in a spot urine sample daily and reported as described in visit 3.

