## 17.0 Data Management and Analysis

17.1 *Describe the data analysis plan, including any statistical procedures. This section applies to both quantitative and qualitative analysis.*

Response: **DATA ANALYSIS**

This is a prospective study to evaluate ketogenic stress before and after 12 week treatment with dapagliflozin and exenatide/Bydureon. The similarities in baseline values between the study groups will be compared using appropriate parametric tests. Transformations of the data on order to meet statistical assumptions may be considered. All statistical analysis will be carried out using SPSS software (SPSS Inc, Chicago, Illinois) based on intention to treat principle. Data will be presented as mean± standard error. *Data will not be imputed to replace missing data and only observed data will used to run the mixed model for repeated measurement (MMRM) analysis. The primary endpoint of the study is to detect a significant difference in the percent change in beta-hydroxybutyrate and acetoacetic acid (total ketone bodies) in the plasma samples following 12 weeks of dapagliflozin treatment compared to placebo. *Fasting samples collected at weeks 0, 1, 4, 8 and 12 will be used for this comparison with values at week 0 considered as baseline. The statistical analysis will be done using MMRM with assigned  $\alpha$  value of 0.05. There is no previous data on effects of dapagliflozin alone on ketone bodies generation in T1D but our preliminary data on 12 weeks treatment with**

dapagliflozin in patients with T1D using insulin and liraglutide shows more than a 2 fold increase in total ketone bodies.

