The secondary end points include the *comparison of the acute changes in AUC0hr-6hr of ketone bodies (plasma and urine), FFA and glucagon between dapagliflozin, exenatide, combination of both and placebo before and after 12 weeks of treatment period using Paired t-test for within group comparisons and student t-test for between groups comparisons.* Additional secondary end points include comparison of basal plasma glucagon, FFA and urinary ketone bodies changes after 12 weeks of dapagliflozin and Bydureon or combination of both treatments compared to baseline using paired t-test and to placebo using 2-way RMANOVA. Changes in insulin dose, glucose levels and carbohydrate intake will be compared after 12 weeks of dapagliflozin and Bydureon treatments to baseline using paired t-test and to placebo with 2-way RMANOVA. Changes in lipolysis mediator (HSL) in plasma and expression of HSL and SGLT-2 in adipose tissue and MNC will be compared to baseline using paired t-test and to placebo with t-test.

*17.2 If applicable, provide a power analysis.*

*NOTE: This may not apply to certain types of studies, including chart/records reviews, survey studies, or observational studies. This question is asked to elicit whether the investigator has an adequate sample size to achieve the study objectives and justify a conclusion.*

*Response:* Conservatively estimating a difference in the change from baseline in ketone bodies generation between the dapagliflozin and placebo of 50%, with standard deviation of no more than 50%, a sample size of 20 patients per group (assuming a drop-out rate of 15%) should provide adequate power ( $\beta = 0.2$ ) to detect a significant difference ( $\alpha = 0.05$ ). A total of 80 patients will be recruited for the study.

*17.3 Describe any procedures that will be used for quality control of collected data.*

*Response:* Data will not be imputed to replace missing data and only observed data will be used to run the mixed model for repeated measurement (MMRM) analysis

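### Secondary endpoints carry within-arm paired t-tests beside between-arm tests, with no statement of which supports a conclusion and no baseline covariate in any of them

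*Combined protocol and SAP*

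**What the plan says.** Section 17.1 describes four secondary families, each with two kinds of test:

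- **Acute AUC over 0 to 6 hours** (plasma and urine ketones, FFA, glucagon), before and after 12 weeks: "Paired t-test for within group comparisons and student t-test for between groups comparisons".
- **Basal plasma glucagon, FFA and urinary ketones**: paired t-test against baseline; two-way repeated-measures ANOVA against placebo.
- **Insulin dose, glucose and carbohydrate intake**: the same pair of methods.
- **Plasma HSL, and HSL and SGLT-2 expression in adipose tissue and mononuclear cells**: changes "will be compared to baseline using paired t-test and to placebo with t-test".

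No sentence ranks the within-arm test against the between-arm test, and no secondary analysis is said to include baseline as a covariate. Apart from changes and repeated measures, the only stated use of baseline values is a check that the groups are similar at entry.

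Section 10.1 bears on how a within-arm change should be read. At Visits 3 to 5, in every arm, "Insulin doses will be titrated to target blood glucose between 70-180 mg/dl if possible at all times". At Visit 2 the baseline samples are drawn after the pump is stopped and before the study drug is given. Only pump users continue to the acute test. Section 4.1 puts 15 patients in each of four arms in cohort 1, and 20 patients in three open-label active groups, without placebo, in cohort 2.

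**The concern.** Hypotheses 1 to 3 in section 1 are claims about one treatment against another. A paired test within one arm cannot answer them, because it adds any drug effect to whatever else changed over the same period.

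This design has several such changes. Insulin is adjusted before dosing and titrated through follow-up in all arms. In the acute test every pump patient, including those on placebo, fasts without insulin for six hours. Section 3.1 itself says that insulin deficiency drives lipolysis, FFA and ketogenesis, so a rise from the pre-dose sample is expected on placebo too. The paired comparison of week 0 AUC with week 12 AUC has a different problem: both AUCs follow a dose of study drug, so it compares drug with drug.

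With both kinds of test listed and neither made decisive, a report could cite a significant change on dapagliflozin and a non-significant one on placebo as if that were a treatment comparison. The preliminary liraglutide results in section 3.1 show that the habit is a live one. Although that study had a placebo group, several results (HbA1c, FFA, glucagon AUC) are given as before-and-after changes with p-values.

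The second issue is precision. Arms are small, and adjusting for a baseline value that is already collected would tighten the between-arm comparisons.

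**Working it through.** **Inputs.** From the documents: 15 per arm in cohort 1 (section 4.1); α = 0.05 for the primary analysis (section 17.1), with none stated for secondary tests. Two-sided testing is assumed. The size of any shared drift and the baseline correlation r are not given, so both are assumed over a range.

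**The plan's own figure.** Section 17.2 takes a difference of 50% and an SD of 50%, so a standardised effect of 50/50 = 1.0, with 80% power and 15% drop-out. The noncentral t gives 17 evaluable per group (power 0.807), and 17/0.85 = 20 per group. The stated 20 reproduces and is not in dispute. No power is stated for any secondary endpoint.

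**Paired test under shared drift and no drug effect.** For a drift of d SDs of the change, the statistic is noncentral t with n − 1 degrees of freedom and noncentrality d√n. The chance that the active arm is significant and placebo is not is p(1 − p), where p is the rejection rate.

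| Drift d | Paired test rejects, n = 15 | Active significant, placebo not, n = 15 | Rejects, n = 12 | Rejects, n = 20 |
|---|---|---|---|---|
| 0 | 5% | 0.05 × 0.95 = 5% | 5% | 5% |
| 0.3 | 19.2% | 0.192 × 0.808 = 16% | 15.8% | 24.7% |
| 0.5 | 43.8% | 0.438 × 0.562 = 25% | 35.3% | 56.5% |
| 0.8 | 82.1% | 0.821 × 0.179 = 15% | 71.4% | 92.4% |

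**Between-arm test under the same drift.** In 100,000 simulated trials at each drift (17 per arm), the t-test on change rejected 4.9% to 5.0% of the time at drifts of 0, 0.3, 0.5 and 0.8. The shared drift cancels. With two time points, the group-by-time term of the repeated-measures ANOVA is the same test.

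**Precision from a baseline covariate.** Let both time points have variance σ² and correlation r. A change has variance 2σ²(1 − r), and the ANCOVA residual has variance σ²(1 − r²). The ratio is (1 − r²)/[2(1 − r)] = (1 + r)/2.

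| Assumed r | ANCOVA / t-test on change | 15 per arm acts like | ANCOVA / t-test with no baseline use, 1 − r² |
|---|---|---|---|
| 0.3 | 0.65 | 15/0.65 = 23 | 0.91 |
| 0.5 | 0.75 | 15/0.75 = 20 | 0.75 |
| 0.7 | 0.85 | 15/0.85 = 18 | 0.51 |

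Estimating the slope costs one degree of freedom and inflates the variance on average by 1 + 1/(30 − 4) = 1.038 with 15 per arm. At r = 0.5 the ratio becomes 0.75 × 1.038 = 0.779, and 15/0.779 is about 19 patients rather than 20.

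The last column matters for acute AUC. The wording there leaves open whether the between-arm t-test uses any baseline at all. In that case r is the correlation of the time-0 concentration with the AUC.

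**The case against.** The strongest reply is that the plan already contains valid tests. Every secondary family has a between-arm comparison, and the hypotheses are comparative. Nothing in section 17.1 says that a conclusion will be drawn from significance in one arm and its absence in another. All of this stands. A reader might infer that shared drift contaminates the secondary analysis as a whole. It does not: between-arm tests of change hold their level.

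A reader might also infer that every between-arm test is a plain t-test and that baseline data are thrown away. Neither is right. Two of the four families use repeated-measures ANOVA, and the HSL/SGLT-2 t-test is on changes, so baseline enters by subtraction. What is absent is covariate adjustment.

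The illustrative figures can be challenged too. The documents give no drift size. Titration plausibly shifts glucose and insulin dose, but there is no stated reason to expect a large drift in adipose SGLT-2 expression. Titration could also differ by arm, though under the no-drug-effect case computed here, blinded arms would be titrated alike on average. Nor is 15 per arm exact for every analysis: cohort 2 adds active-arm patients, drop-out of 15% is planned, and acute AUC comes from pump users only. These points make the percentages illustrative. They do not turn a paired test into evidence of a drug effect.

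Finally, ANCOVA is an efficiency gain on endpoints with no stated power, not a repair of an invalid test. That is a fair description of that half of the point.

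**Conclusion.** The point holds in a limited form. The plan leaves open whether secondary drug-effect conclusions come from a valid between-arm comparison or from a paired test that cannot supply them, and no secondary analysis is stated to adjust for baseline as a covariate.

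The false-positive rates for the paired test (19%, 44% and 82% at n = 15) rest on assumed drifts of 0.3, 0.5 and 0.8 SD; with no drift the rate is 5%. The variance ratios (0.65, 0.75, 0.85) rest on assumed correlations of 0.3, 0.5 and 0.7 and equal variance at both times. The direction does not depend on those choices: (1 + r)/2 is below 1 for any r below 1, apart from the small cost of one degree of freedom. With 15 per arm, that cost would cancel the gain only when r exceeds 2/1.038 − 1, about 0.93.

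The documents do not support a finding that the planned between-arm tests are biased, or that the investigators plan to infer effects by comparing p-values across arms. Cohort 2 has no placebo group, so its within-arm changes have no concurrent placebo control.

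**What to change.** In section 17.1:

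1. State that secondary conclusions rest only on between-arm contrasts, and that paired within-arm tests are descriptive.
2. Replace the between-arm t-tests for acute AUC and HSL/SGLT-2 with ANCOVA, using the week 0 pre-dose value as covariate. For AUC, at both week 0 and week 12, use the week 0 time-0 concentration. The week 0 AUC is already on drug, and the week 12 time-0 sample follows 12 weeks of treatment.
3. Adjust the two repeated-measures ANOVA families in the same way, by ANCOVA at week 12 or by MMRM with baseline as covariate. MMRM is already the method for the primary endpoint.
4. Treat within-arm changes in cohort 2 as descriptive.
5. Say what happens when the covariate is missing. The dedicated mononuclear-cell draws in section 10.1 are listed from 1 hour onward with no time-0 draw named, and a biopsy is not done after recent aspirin or NSAID use.

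The cost is analysis wording and one degree of freedom per model. No new visits or patients are needed, and no new samples except possibly a pre-dose mononuclear-cell sample, if item 5 shows that none is taken. The change should be made before unblinded endpoint data are examined. Section 19.7 provides for one endpoint review after half the patients have completed.

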## 4.0 Study Design

### 4.1 Describe and explain the study design (e.g. case-control, cross-sectional, ethnographic, experimental, interventional, longitudinal, observational).

*Response:* The first 60 patients (cohort 1) will be involved in a single center, prospective, double blind, randomized, placebo –controlled in a parallel design study. The last 20 patients (cohort 2) will be enrolled into a single centered, prospective, randomized, open labeled study. The study will be conducted at the Diabetes – Endocrinology Center of Western New York under the direction of [name], M.D, [name], MD, [name] and [name], PhD.

In the first cohort, sixty (60) patients with T1D will be enrolled and randomized into 4 groups (15 each) to receive placebo, or dapagliflozin, or exenatide (5µg acutely)/Exenatide extended release (2mg weekly subcutaneous injection, long term), or exenatide (5µg acutely)/Exenatide extended release (2mg weekly subcutaneous injection, long term) and dapagliflozin treatments acutely and for 12 weeks.

The treatment arms of this study are:

1. Placebo Arm: dapagliflozin placebo (oral tablet) and exenatide (5µg acutely)/Exenatide extended release (long term) placebo (subcutaneous injection)
2. Dapagliflozin Arm: dapagliflozin 10mg (oral tablet) and exenatide (5µg acutely)/Exenatide extended release (long term) placebo (subcutaneous injection)
3. Exenatide/Exenatide extended release Arm: subcutaneous injection of Exenatide (5µg acutely)/Exenatide extended release 2 mg weekly injection (long term) and dapagliflozin placebo
4. Exenatide/Exenatide extended release & dapagliflozin Arm: Exenatide (5µg acutely)/Exenatide extended release 2 mg weekly injection (long term) and dapagliflozin 10mg

In the second cohort, twenty (20) patients will be randomized into three groups.

1. Open-label Dapagliflozin
2. Open-label Bydureon/Byetta
3. Open label Bydureon/Byetta and open label Dapagliflozin

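### The 80% power claim assumes 20 patients per group, but only 15 are randomised to placebo; on the plan's own inputs the primary comparison has about 68% to 76% power

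*Combined protocol and SAP*

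**What the plan says.** The primary endpoint in section 17.1 compares the percent change in total plasma ketone bodies over 12 weeks between dapagliflozin and placebo, using MMRM at alpha 0.05.

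Section 17.2 sizes the trial for that comparison. It assumes a "difference in the change from baseline in ketone bodies generation between the dapagliflozin and placebo of 50" per cent, "with standard deviation of no more than 50" per cent. It then states that "a sample size of 20 patients per group (assuming a drop-out rate of 15%) should provide adequate power", with beta of 0.2, and concludes that "A total of 80 patients will be recruited for the study". Four groups of 20 make 80.

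Section 4.1 describes a two-cohort allocation. In the blinded cohort, "sixty (60) patients with T1D will be enrolled and randomized into 4 groups (15 each"), one arm being placebo. Then, "In the second cohort, twenty (20) patients will be randomized into three groups": dapagliflozin, exenatide, and the combination, all open label. Section 10.1 likewise names only active treatments for cohort 2. Section 5.1 confirms the total of 80.

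**The concern.** The two sections agree on the total of 80 but not on how it is divided. Cohort 2 adds no placebo patients, so the placebo arm stays at 15, and placebo is one side of the only comparison the power statement covers. The statement was not adapted to the two-cohort allocation.

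The plan also does not say whether open-label cohort 2 patients enter the primary comparison, or in what ratio cohort 2 is divided. The group sizes behind the primary test therefore cannot be read from the document.

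What is at stake is how the result is interpreted. The trial was motivated by ketoacidosis seen with an SGLT2 inhibitor in type 1 diabetes. A non-significant ketone result would be read as coming from a study with a 20% chance of missing a 50-point difference, when on the plan's own inputs that chance is higher.

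**Working it through.** **Inputs**
- Difference 50 points and SD 50 (section 17.2), so the standardised difference is d = 50/50 = 1.0.
- Alpha 0.05 (sections 17.1 and 17.2). Sidedness is not stated. Two-sided is assumed, because it reproduces 20 per group, whereas a one-sided test would need only 13 evaluable per group by the normal approximation.
- Dropout 15% (section 17.2).
- Placebo 15 and dapagliflozin 15 in cohort 1 (section 4.1).
- Cohort 2: 20 patients in three groups. No ratio is given, so an equal split is assumed: 20/3 = 6.67 on dapagliflozin alone.

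**Method.** Two-sample t-test, noncentral t distribution:
- noncentrality = d / √(1/n₁ + 1/n₂), with df = n₁ + n₂ − 2
- power = P(|T| > t₀.₉₇₅,df)

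**Step 1: the plan's own figure.** 20 × 0.85 = 17 evaluable per group. Noncentrality = 1/√(2/17) = 2.916, df = 32, critical value 2.037. Power = **80.7%**. In reverse, 17/0.85 = 20. The stated size reproduces, so this is evidently the calculation behind section 17.2.

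**Step 2: blinded cohort alone.** 15 × 0.85 = 12.75 evaluable per arm. Noncentrality = 1/√(2/12.75) = 2.525, df = 23.5. Power = **67.8%**.

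**Step 3: both cohorts pooled.** Dapagliflozin 15 + 6.67 = 21.67, and 21.67 × 0.85 = 18.42 evaluable, against 12.75 on placebo. Noncentrality = 1/√(1/12.75 + 1/18.42) = 2.745, df = 29.2. Power = **75.6%**.

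**Step 4: difference detectable with 80% power at SD 50** (solved numerically): **57.9** points for cohort 1 alone and **52.8** points pooled.

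**Sensitivity**

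| Evaluable placebo v dapagliflozin | t-test | Normal approximation |
|---|---|---|
| 17 v 17 (as stated) | 80.7% | 83.0% |
| 12.75 v 12.75 (cohort 1) | 67.8% | 71.4% |
| 13 v 13 (whole patients) | 68.7% | 72.2% |
| 12.75 v 18.42 (pooled) | 75.6% | 78.4% |
| 13 v 18 (whole patients) | 75.7% | 78.5% |
| 15 v 15 (cohort 1, no dropout) | 75.3% | 78.2% |
| 15 v 21.67 (pooled, no dropout) | 82.5% | 84.6% |

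- Unequal cohort 2 split: if 5 to 8 patients receive dapagliflozin alone, pooled power runs from 74.1% to 76.7%.
- Error degrees of freedom taken from all four arms: 81.9% as stated, 77.1% pooled, 69.6% for cohort 1.

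**The case against.** The mismatch in group size is not in dispute. The case against concerns how firm the power figure is and how much it matters.

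- **The inputs are described as cautious.** The SD is given as an upper limit and the difference as conservative. Power of 80% returns at an SD of 47.4 pooled or 43.2 for cohort 1 alone. That is correct, but the plan claims its 80% at an SD of 50, so the loss relative to that claim remains whichever SD is true. Section 17.1 also says there are no earlier data on dapagliflozin alone in this population.
- **MMRM keeps patients who leave early.** Someone who drops out after week 1 still contributes, so removing the full 15% may overstate the loss. This is fair, but the documents give no correlations with which to size the gain, and section 17.2 itself makes the full dropout allowance. Without any dropout the pooled comparison would reach 82.5%; cohort 1 alone would still reach only 75.3%.
- **The pooled shortfall is small.** It is about 2 to 4 points below 80%, depending on method. This stands. However, the plan nowhere says the cohorts are pooled, and pooling sets open-label patients without concurrent placebo against blinded placebo patients.
- **Limited consequence.** The error leaves type I error, the estimate, its confidence interval and the total of 80 untouched, and an interval would show the precision actually achieved. This is also true. It limits the harm to the claim of adequacy, but that claim is the purpose of section 17.2.

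One point changes the remedy: the cohort 2 split and the primary analysis set must be stated before a single power figure can be given.

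**Conclusion.** The concern holds. The power statement rests on a placebo group of 20 that the design does not provide. On the plan's own inputs, power is about 68% in the blinded cohort and about 76% if both cohorts are pooled, so the type II error is about 32% or 24%, not 20%.

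These figures assume two-sided testing, an equal three-way split of cohort 2 (for the pooled figure), 15% dropout contributing no information, and a simple two-sample comparison. The normal approximation and the four-arm error degrees of freedom also leave both scenarios below 80%. Only pooling with little or no effective loss to dropout would bring power back to 80% at the stated difference and SD.

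**What to change.** 1. In section 17.1, state whether the primary comparison uses cohort 1 alone or both cohorts.
2. In section 4.1, state how the 20 cohort 2 patients are divided.
3. In section 17.2, remove the figure of 20 per group and give the real sizes: placebo 15 (about 13 completers), with dapagliflozin either 15 (about 13 completers) from cohort 1 alone or about 21 to 22 (about 18 completers) if pooled with an equal split.
4. State the matching power, about 68% or about 76%, or the detectable difference, about 58 or 53 points. State that the test is two-sided. If a gain from MMRM is claimed, give the correlations assumed.

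The cost is wording only. No patients, visits or procedures are added. The stated power becomes less favourable.
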